2.2 Secondary

- 2.2.1. Late grade ≥ 2 GI and/or GU toxicities of interest within 24 months after the protocol RT, using the CTCAE v4.0.
- 2.2.2. Acute grade ≥ 3 GI and/or GU toxicities of interest during and within 3 months after the protocol RT, using the CTCAE v4.0.
- 2.2.3. Disease-free survival including freedom from PSA relapse at 5 years
- 2.2.4. Disease-specific survival at 5 years
- 2.2.5. Overall survival at 5 years

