3.2 Exclusion Criteria

- 3.2.1. Any known nodal (N1) or distant metastasis (M1)
- 3.2.2. Previous androgen deprivation therapy lasting more than 6 months
- 3.2.3. History of inflammatory bowel disease
- 3.2.4. Presence of a hip prosthesis
- 3.2.5. Prior pelvic radiotherapy or prostatectomy
- 3.2.6. Prior or concurrent antineoplastic agents (chemotherapy)
- 3.2.7. Previous or concurrent malignancy other than non-melanoma skin cancer within 5 years of diagnosis of prostate cancer.
- 3.2.8. Inability to start the protocol treatment within 1 month after study enrollment.
- 3.2.9. Medical or psychiatric conditions that preclude informed decision-making or compliance with the protocol treatment or follow-up

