7.1. Proton beam therapy

7.1.1 Treatment planning

7.1.1.1 Preparation prior to simulation

A minimum of 1 day prior to a scheduled CT simulation, a total of four carbon markers are implanted into the prostate gland (two in the left and two in the right lobe of the prostate gland), via transperineal approach, under a transrectal ultrasound guidance by a radiologist. These implanted carbon markers are used for daily image-guided proton beam therapy.

Bladder preparation: A patient is to void one hour before simulation or treatment. Right after voiding, he drinks 250 or 500 mL (8.5 or 16.9 oz) of water over the following 15 minutes. Then he does not void until he completes a CT simulation or treatment. This systemic approach is to minimize day-to-day variation of bladder volume as much as possible.

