The investigator will review all adverse event reports to determine if specific reports need to be made to the IRB and FDA. The investigator will sign and date the adverse event report when it is reviewed. For this protocol, only directly related SAEs/UPIRTSOs will be reported to the IRB.

10.4 CTCAE v4.0 is used for the following AEs to be graded at each evaluation and pretreatment symptoms/conditions to be evaluated at baseline:

System Organic Class	Adverse events/Symptoms
Gastrointestinal	Diarrhea
	Fecal incontinence
	Proctitis
	Rectal hemorrhage
	Rectal ulcer
	Small intestinal obstruction

	Stricture/Stenosis: Rectum
Renal/Genitourinary	Bladder spasm
	Hematuria
	Urinary frequency
	Urinary incontinence
	Urinary tract obstruction
	Urinary tract pain
	Urinary urgency
	Cystitis noninfective
	Urinary retention
Sexual/Reproductive function	Erectile dysfunction

Acute AEs are defined as those that occur from day 1, or commencement of radiation therapy, through 3 months after the completion of protocol treatment.

All AEs seen after 3 months after the completion of protocol treatment are considered late effects.

10.4.1 Submit via appropriate reporting mechanisms (i.e., paper or electronic) the following AEs experienced by a patient and not specified in Section 10.4:

Grade 5 AEs (Death)

10.4.1.1.1 Any death within 30 days of the patient's last study treatment or procedure regardless of attribution to radiation treatment

10.4.1.1.2 Any death more than 30 days after the patient's last study treatment or procedure that is felt to be at least possibly related to radiation treatment must also be submitted as a Grade 5 AE, with a CTCAE type and attribution assigned.

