16.3 Analysis Plan

16.3.1 Primary Outcome Analyses:

16.3.1.1 Definition: The primary endpoint of this trial is the proportion of patients who experience a late grade 3 or higher GI or GU toxicity. Toxicity will be defined as an adverse event possibly, probably, or definitely related to proton beam therapy. A late GI or GU toxicity will be defined as a GI or GU toxicity that occurs between 3 months and 2 years from the completion of proton beam therapy. All patients meeting the eligibility criteria who have signed a consent form and have begun treatment will be evaluable for late toxicity, with the exception of patients determined to be a major violation.

16.3.1.2 Estimation: The proportion of grade 3 or higher GI or GU toxicities will be estimated by the number of patients with a late grade 3 or higher GI or GU toxicity divided by the total number of evaluable patients. Exact binomial 95% confidence intervals for the toxicity proportion will be calculated.

16.3.2 Secondary Outcome Analyses:

16.3.2.1 Disease-free survival is defined as the time from registration until the time of the first occurrence of biochemical failure (Section 11.2.1), local recurrence, regional recurrence, distant metastases, or death due to any cause. The distribution of disease-free survival will be estimated using the method of Kaplan-Meier. The disease-free survival rate will be estimated at 2 years and 5 years.

16.3.2.2 Disease-specific survival is defined as the time from registration until the date of death due to prostate cancer (Section 11.2.6). The distribution of disease-specific survival will be estimated using the method of Kaplan-Meier. The disease-specific survival rate will be estimated at 2 years and 5 years.

16.3.2.3 Overall survival is defined as the time from registration until the death due to any cause (Section 11.2.7). The distribution of overall survival will be estimated using the method of Kaplan-Meier. The overall survival rate will be estimated at 2 years and 5 years.

16.3.2.4 An acute adverse event is defined as an adverse event that occurs any time between registration and 3 months after the completion of proton beam therapy. The rate of \geq grade 3 GI or GU acute adverse events will be estimated by the number of patients with a \geq grade 3 GI or GU acute adverse event divided by the total number of evaluable patients. Exact binomial 95% confidence intervals for the true rate of \geq grade 3 GI or GU acute adverse events will be calculated.

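### The acute toxicity analysis in Section 16.3.2.4 counts any-cause events from registration, while objective 2.2.2 and Section 10.4 start at radiotherapy; the secondary acute rate can only be equal to or above the one intended

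*Combined protocol and SAP*

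**What the plan says.** The acute period is described in three places in the current text.

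- **Objective 2.2.2** covers grade 3 or higher GI and/or GU toxicities "during and within 3 months after the protocol RT".
- **Section 10.4** defines acute events as "those that occur from day 1, or commencement of radiation therapy, through 3 months after the completion of protocol treatment".
- **Section 16.3.2.4**, the analysis, takes any adverse event "that occurs any time between registration and 3 months after the completion of proton beam therapy" and divides the number of patients with one of grade 3 or higher, GI or GU, by the number evaluable.

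For the primary (late) endpoint, Section 16.3.1.1 adds a filter: "Toxicity will be defined as an adverse event possibly, probably, or definitely related to proton beam therapy". Sections 16.3.2.4 (acute) and 16.3.2.5 (late grade 2 or higher) have none. Section 16.3.2.6 says only that relationship to treatment will be considered when the frequency tables are reviewed. For the acute and late definitions it points to 16.3.2.2 and 16.3.2.3, which define disease-specific and overall survival.

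There can be a gap between registration and the first fraction. Exclusion 3.2.8 reads "Inability to start the protocol treatment within 1 month after study enrollment". Under Section 7.1.1.1, before simulation, "a total of four carbon markers are implanted into the prostate gland". Section 7.1.1.2 allows a bladder catheter at simulation when contrast is used.

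**The concern.** A statistician programming from Section 16 would estimate a quantity other than the one in objective 2.2.2. It differs in two ways: the window opens earlier, and events unrelated to proton therapy count.

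The early interval may contain invasive steps. Hematuria, urinary retention and urinary tract pain are all graded terms in Section 10.4, and a grade 3 event of this kind after marker implantation or catheterisation would enter the acute rate if it fell after registration. At stake is the reading of the secondary acute rate as a property of the proton regimen, and an avoidable choice between definitions once the data are in hand.

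**Working it through.** **Step 1. The plan's own figures.** The only design figures are those in Section 16.2.4 for the late endpoint: the regimen is promising if 4 or fewer of 51 patients have an event. With P(X ≤ 4) = Σ C(51,k) p^k (1−p)^(51−k), k = 0 to 4:

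| True late rate | Plan | Recomputed |
|---|---|---|
| 0.20 | 0.02 | 0.0159 |
| 0.15 | 0.10 | 0.1022 |
| 0.10 | 0.41 | 0.4131 |
| 0.05 | 0.89 | 0.8896 |

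All four agree to two decimals. None depends on the acute window, because late events start 3 months after proton therapy ends. No design figure is given for the acute rate.

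**Step 2. The definitions side by side.**

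| Section | Start | End | Attribution |
|---|---|---|---|
| 2.2.2 | Radiotherapy | 3 months after radiotherapy | Toxicities; term not defined there |
| 10.4 | First radiotherapy day | 3 months after protocol treatment | None stated |
| 16.3.2.4 | Registration | 3 months after proton therapy | None |
| 16.3.1.1 (late, primary) | 3 months after proton therapy | 2 years | At least possible |
| 16.3.2.5 (late grade 2 or higher) | 3 months after proton therapy | 2 years | None |

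The end of the window also differs in wording. Section 7.0 makes androgen deprivation part of protocol treatment. With 28 months of it, started 2 months before a 5-week (1.15-month) course, it would end 28 − 2 − 1.15 = 24.85 months after radiotherapy. Read literally, the acute period in Section 10.4 would then run past the 2-year limit of the late window. That cannot be intended.

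**Step 3. Direction.** Let A be the patients with an at least possibly related event between the first fraction and 3 months after proton therapy. Let B be those with an event of any cause between registration and the same end. Every patient in A is in B, so with a common denominator |B|/n ≥ |A|/n. The evaluability rule (treatment begun) restricts which patients count, not which event dates count, so it does not close the gap.

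**Step 4. Size.** A patient in B but not in A adds 1/51 = 2.0 points, or 1/56 = 1.8 points if all 56 planned accruals enter the final estimate (Section 16.3.4 includes over-accrued patients). Exact 95% intervals with n = 51:

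| Patients | Rate | 95% CI |
|---|---|---|
| 0 | 0.0% | 0 to 7.0% |
| 1 | 2.0% | 0.0 to 10.4% |
| 2 | 3.9% | 0.5 to 13.5% |
| 3 | 5.9% | 1.2 to 16.2% |

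The documents give no rate for events before the first fraction. For **assumed** per-patient rates q, the chance that at least one of 51 patients has such an event is 1 − (1−q)^51:

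| Assumed q | Chance of at least one |
|---|---|
| 0.5% | 23% |
| 1% | 40% |
| 2% | 64% |
| 4% | 88% |

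These show sensitivity only; they are not forecasts.

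**The case against.** The strongest case against is that this is a wording mismatch in a descriptive rate with no hypothesis or threshold. Event date and relationship are recorded (Sections 10.2.2 and 10.3), so either version can be computed later. All-cause counting is a defensible conservative choice in a single-arm safety study. Marker implantation stands within Section 7.1, so its complications might be regarded as part of the regimen. The documents do not say whether implantation follows registration, and the catheter is optional.

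Most of this stands, and it keeps the severity low. It does not remove the conflict. If the sponsor wants preparation events or all-cause events in the acute rate, objective 2.2.2 and Section 10.4 should say so. The objection also shows that adding a filter to 16.3.2.4 alone would leave it inconsistent with 16.3.2.5, which has the same gap.

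A reader might infer three stronger points that the documents do not support:

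- **Androgen deprivation inflates the early interval.** Section 7.2 says it usually starts 2 months before proton therapy. If proton therapy starts within 1 month of enrollment, androgen deprivation usually predates registration and runs through both windows, so moving the start removes little of it. No section links it to the graded GU terms.
- **Stable baseline symptoms would be counted, or the early interval is ungraded.** Section 10.1 records a preexisting condition as an adverse event only if it worsens, and Section 18.1 lists baseline and on-study adverse event forms.
- **The rate is inflated by 24%.** With a full 1-month gap the window is (1 + 1.15 + 3)/(1.15 + 3) = 5.15/4.15 = 1.24 times as long. That is a ratio of calendar time under the longest such gap, not of events; risk before radiotherapy need not equal risk during it.

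**Conclusion.** The concern holds as an inconsistency of definition. As written, Section 16.3.2.4 does not estimate objective 2.2.2, and its result can only be equal to or higher than the intended rate. Each patient counted solely for a pre-radiotherapy or unrelated event adds about 2.0 points. How many there would be cannot be derived from the documents; the number may be zero.

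The conclusion rests on three assumptions. The toxicities in objective 2.2.2 carry the meaning given in Section 16.3.1.1. Some procedures or events fall between registration and the first fraction. The 1-month limit in 3.2.8 refers to proton therapy; if it also covers androgen deprivation, as Section 7.0 would allow, the gap could be longer.

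A reader might also infer that the trial's main conclusion is at risk. It is not: the primary endpoint, the rule of 5 or more in 51 and the stopping rules in Section 16.4.2 all concern late events and already require at least possible attribution. Severity is low.

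**What to change.** 1. In 16.3.2.4, start the window at the first proton fraction and keep its end at 3 months after completion of proton therapy.
2. In 10.4, tie the end of the acute period, and so the start of the late period, to completion of proton therapy rather than protocol treatment.
3. Apply the attribution definition of 16.3.1.1 to both 16.3.2.4 and 16.3.2.5. Report all-cause rates alongside, and list events between registration and the first fraction separately.
4. In 16.3.2.6, correct the cross-reference to 16.3.2.4 and 16.3.2.5.

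The cost is a few sentences in an amendment. No new data are needed, since event date and attribution are already collected, and the sample size and decision rule do not change. The downside is that the headline acute rate may be slightly lower than an all-cause count; the separate listing keeps that information in view.

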10.0 Adverse Event (AE) Reporting and Monitoring

10.1 Definitions

Adverse Event- An untoward or undesirable experience associated with the use of a medical product (i.e. drug, device, biologic) in a patient or research subject.

Serious Adverse Event - Adverse events are classified as serious or non-serious. Serious problems/events can be well defined and include;

- death
- life threatening adverse experience
- hospitalization secondary to radiation treatment, RT side effects or problem due to prostate carcinoma
- inpatient, new, or prolonged; disability/incapacity
- persistent or significant birth defect/anomaly

and/or per protocol may be problems/events that in the opinion of the investigator may have adversely affected the rights, safety, or welfare of the subjects or others, or substantially compromised the research data.

All adverse events that do not meet any of the criteria for serious, should be regarded as non-serious adverse events.

Unanticipated Problems Involving Risks to Subjects or Others (UPIRTSO) - Any unanticipated problem or adverse event that meets the following three criteria:

- **Serious**: Serious problems or events that result in significant harm, (which may be physical, psychological, financial, social, economic, or legal) or increased risk for the subject or others (including individuals who are not research subjects). These include: (1) death; (2) life threatening adverse experience; (3) hospitalization - inpatient, new, or prolonged; (4) disability/incapacity - persistent or significant; (5) birth defect/anomaly; (6) breach of confidentiality and (7) other problems, events, or new information (i.e. publications, DSMB reports, interim findings, product labeling change) that in the opinion of the local investigator may adversely affect the rights, safety, or welfare of the subjects or others, or substantially compromise the research data, **AND**
- **Unanticipated**: (i.e. unexpected) problems or events are those that are not already described as potential risks in the protocol, consent document, or not part of an underlying disease. A problem or event is "unanticipated" when it was unforeseeable at the time of its occurrence. A problem or event is "unanticipated" when it occurs at an increased frequency or at an increased severity than expected, **AND**
- **Related**: A problem or event is "related" if it is possibly related to the research procedures.

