10.2.2 Assessment of Attribution

When assessing whether an adverse event is related to a medical treatment or procedure, the following attribution categories are utilized:

Definite - The adverse event is clearly related to the agent(s).

Probable - The adverse event is likely related to the agent(s).

Possible - The adverse event may be related to the agent(s).

Unlikely - The adverse event is doubtfully related to the agent(s).

Unrelated - The adverse event is clearly NOT related to the agent(s).

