16.3.2.5 A late adverse event is defined as an adverse event that occurs any time between 3 months and 2 years after completion of proton beam therapy. The rate of \geq grade 2 GI or GU late adverse events will be estimated by the number of patients with a \geq grade 2 GI or GU late adverse event divided by the total number of evaluable patients. Exact binomial 95% confidence intervals for the true rate of \geq grade 2 GI or GU late adverse events will be calculated.

16.3.2.6 Adverse Events: All eligible patients that have initiated treatment will be considered evaluable for assessing adverse event rate(s). The maximum grade for each type of adverse event will be recorded for each patient, and frequency tables will be reviewed to determine patterns. Additionally, the relationship of the adverse event(s) to the study treatment will be taken into consideration. Acute and late adverse events (as defined in sections 16.3.2.2 and 16.3.2.3) will be summarized separately.

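### The secondary acute and late rates count adverse events with no attribution condition, although the goals they serve concern treatment-related toxicity

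*Combined protocol and SAP*

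**What the plan says.** All references are to the combined protocol and SAP.

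- **Goals.** Goal 2.2.1 is late grade 2 or higher "GI and/or GU toxicities of interest within 24 months after the protocol RT". Goal 2.2.2 uses the same term for acute grade 3 or higher events, during treatment and for 3 months afterwards.
- **Meaning of toxicity.** Sections 16.1.1 and 16.3.1.1 both state: "Toxicity will be defined as an adverse event possibly, probably, or definitely related to proton beam therapy". The primary late grade 3 or higher rate rests on this definition.
- **Late secondary rate.** Section 16.3.2.5 states: "A late adverse event is defined as an adverse event that occurs any time between 3 months and 2 years", with time measured from the end of treatment. The rate is the number of patients with at least a "grade 2 GI or GU late adverse event divided by the total number of evaluable patients", with an exact binomial 95% interval.
- **Acute secondary rate.** Section 16.3.2.4 has the same structure for grade 3 or higher events, with a window from registration to 3 months after treatment.
- **Attribution.** Section 10.2.2 grades every adverse event on five levels from definite to unrelated. Section 16.3.2.6 says that relationship to treatment will be considered when adverse events are summarised, without saying how.

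**The concern.** The change from toxicity to adverse event changes who is counted. Section 10.2.2 lets an investigator record an adverse event as unlikely to be related or as unrelated, so the broader term does not imply a causal link. Two things follow.

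First, the estimators in Sections 16.3.2.4 and 16.3.2.5 do not estimate what Goals 2.2.2 and 2.2.1 name. Second, two late rates over the same period, one at grade 3 or higher and one at grade 2 or higher, would be reported on different bases. A reader would naturally subtract one from the other to see how many men had grade 2 toxicity at worst, and that subtraction would not be valid.

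The secondary endpoints are to be reported publicly (Section 16.6), and Section 1.8 presents the results as a possible basis for a phase III trial. The late grade 2 or higher rate is therefore likely to be quoted as a toxicity rate.

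**Working it through.** **The plan's own figures.** No figure is stated for either secondary rate. The stated figures belong to the primary design: the regimen is promising if 4 or fewer of 51 evaluable patients have a late grade 3 or higher toxicity. The formula is P(X ≤ 4) = Σ C(51,k) p^k (1 − p)^(51−k), summed over k = 0 to 4.

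| True rate p | Stated (16.2.4) | Recomputed |
|---|---|---|
| 0.20 | 0.02 | 0.0159 |
| 0.15 | 0.10 | 0.1022 |
| 0.10 | 0.41 | 0.4131 |
| 0.05 | 0.89 | 0.8896 |

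All four agree to two decimals. They depend only on the primary endpoint, which carries its own attribution condition, so nothing below changes them.

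**The definitions side by side.**

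| Section | Term | Attribution condition |
|---|---|---|
| 2.2.1, 2.2.2 (goals) | toxicities | none of its own; carried by the term |
| 16.1.1, 16.3.1.1 (primary) | toxicity | possible, probable or definite |
| 16.3.2.4 (acute, grade 3 or higher) | adverse event | none |
| 16.3.2.5 (late, grade 2 or higher) | adverse event | none |
| 16.3.2.6 (summaries) | adverse event | to be considered; no counting rule |
| 16.4.2 (stopping rule) | adverse event | possible, probable or definite |

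The stopping rule shows that where the plan uses the broader term and wants related events only, it can say so. Sections 16.3.2.4 and 16.3.2.5 do not.

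**Effect on the late rates.** Among n evaluable patients, let A be those with a related late event of grade 2 or higher, C the subset of A with a related event of grade 3 or higher, and B those whose only late events of grade 2 or higher are unrelated.

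- Primary rate: C/n.
- Section 16.3.2.5, read plainly: (A + B)/n.
- Difference: (A − C)/n + B/n.

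The first term is the share of men whose worst related event was grade 2. The second is the distortion. It includes unrelated events of grade 3 or higher, which the primary rate excludes.

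**Size.** Each patient in B adds 1/51 = 1.96 points, or 1/56 = 1.79 points if all 56 planned patients enter the final estimate under Section 16.3.4. The documents give no value for B. The counts below are assumptions chosen only to show the scale, with A = 8 and n = 51 (exact 95% intervals):

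| B (assumed) | Reported rate | 95% CI |
|---|---|---|
| 0 | 8/51 = 15.7% | 7.0 to 28.6% |
| 2 | 10/51 = 19.6% | 9.8 to 33.1% |
| 5 | 13/51 = 25.5% | 14.3 to 39.6% |
| 10 | 18/51 = 35.3% | 22.4 to 49.9% |

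**Can such events arise?** Section 11.2.2 counts haematuria from cancer progression and obstruction by tumour as signs of local recurrence. Haematuria and urinary tract obstruction are also among the terms graded under Section 10.4. A tumour-caused event at or above the grade threshold would therefore meet the literal counting rule. In Section 16.3.2.4 the window opens at registration, before the first fraction, so an event that precedes proton therapy would meet it too.

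**The case against.** The strongest reply is that Section 16.3.2.5 is silent on attribution and does not declare an all-cause rate. Where the protocol wants events counted whatever their cause it can say so, as Section 10.4.1.1.1 does for deaths within 30 days. Section 10.1 also describes an adverse event as "An untoward or undesirable experience associated with the use of a medical product", which could be taken to imply a link with treatment, and Section 16.3.2.6 mentions relationship. A related-only reading is therefore available. This stands as far as intent goes: one cannot say that the authors chose an all-cause rate. It does not supply a rule. Section 10.2.2 has categories for unrelated adverse events, so the Section 10.1 wording cannot settle attribution. Section 16.3.2.6 does not say which categories enter a numerator, and its cross-references for acute and late events lead to the survival definitions.

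Conversely, Goals 2.2.1 and 2.2.2 state no attribution themselves. It reaches them through the word toxicities, and the definition of that word sits in the primary endpoint text. This is true, but it is the only definition of the term in the documents.

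An all-attribution rate is also a defensible, conservative choice in a single-arm study, where attribution is a matter of judgement. That is a reason to report it as well, not to leave the basis unstated.

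A reader might infer that background bowel and urinary symptoms in older men will inflate the rate by a predictable number of points. The documents do not support this. Section 10.1 records a preexisting condition as an adverse event only if it worsens, and Section 10.4 has symptoms evaluated at baseline, so stable complaints should not count. New or worsened events from other causes still would, but their frequency is not given. Tables 4 and 5 do not help: they use RTOG and modified LENT/RTOG criteria rather than CTCAE v4.0, and they do not separate unrelated events.

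**Conclusion.** The mismatch is real and affects both secondary toxicity rates. As written, Sections 16.3.2.4 and 16.3.2.5 count adverse events by grade and time window, while the goals they serve concern toxicities, which the plan defines as at least possibly related to proton beam therapy. The late grade 2 or higher and late grade 3 or higher rates would not form one severity scale.

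This rests on two readings: that the definition in Sections 16.1.1 and 16.3.1.1 governs the same word in the goals, and that an estimator with no attribution condition applies none. Both are the plain readings, though neither is spelled out.

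The effect is about 2 points for each patient whose only qualifying event is unrelated, and the number of such patients is unknown. It could be zero. A reader might also infer that the trial's conclusion is at risk. It is not: neither secondary rate has a hypothesis test or threshold, and the primary endpoint and the stopping rule both state attribution. Sample size and power are unchanged.

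**What to change.** Add one sentence to each of Sections 16.3.2.4 and 16.3.2.5. It should say that the rate answering Goal 2.2.2 or 2.2.1 counts patients with an adverse event at least possibly related to proton beam therapy, as in Section 16.3.1.1, and that the rate regardless of attribution is reported beside it with its own exact 95% interval. Both sections need the change; amending only the late rate would leave the acute and late rates on different bases.

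The cost is two sentences and one extra line per table. Attribution is already assessed under Section 10.2.2 and listed for the adverse event worksheet in Section 10.3, so no new data are needed and the design does not change. The sentences should be in place before the secondary rates are analysed, so that the choice of basis is not made with the results in view.
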